## BODY AND SOCIAL BEHAVIOR (BSB)

needed to run sessions (IDS, CTRC) were closed. We also wanted to avoid the height of influenza season, which the CDC stated was January-February of that year.

### 4. Variables

#### Manipulated variables:

- **Inflammation.** All participants were assigned to receive either the active influenza vaccine (0.5 mL FluLaval Quadrivalent) or a sham vaccine (0.5 mL Sodium Chloride, i.e., saline) during session 1. At both sessions 1 and 2, approximately 6 mL of blood were collected via venipuncture. Final plasma samples were assayed for Interleukin-6 (IL-6), Interleukin-10 (IL-10), Interferon-Gamma (IFN- $\gamma$ ), and Tumor Necrosis Factor-Alpha (TNF- $\alpha$ ) using a Simple Plex Cartridge Kit from R&D systems Inc. (Minneapolis, MN) containing IFN-gamma 3rd gen, IL-10 2nd gen, IL-10 2nd gen, IL-6 3rd gen, TNF-alpha 2nd gen cartridges for use with Human Plasma/Serum.

#### Measured variables/Indices:

##### Session 1

- **Self-report questionnaires:**
  - **Valence, Arousal, Dominance:** participants responded to prompts asking “how [pleasant or unpleasant/ activated or deactivated/ submissive (without control) or dominant (in control)] do you feel right now.”
  - **Open ended feelings report:** Participants responded to the prompt, “Please write out in your own words how you feel right now. Please be as SPECIFIC and DESCRIPTIVE as possible about how you feel” using a free-text field.
  - **Sickness Symptoms** (Andreasson et al., 2018).
  - **Daily Health Behaviors:** Participants reported on exercise, sexual activity, and consumption of caffeine, cigarettes, other nicotine products, alcohol, and medications over the past 24-48 hours.
  - **Adapted Brief Pittsburgh Sleep Quality Index** (Sancho-Domingo et al., 2021; Gordon & Chen, 2016)
  - **RU-SATED Scale** (Buyssse, 2014).
  - **Interoception Sensory Questionnaire** (Fiene et al., 2018)
  - **Two-way social support Scale** (Shakespeare-Finch & Obst, 2011)
  - **Physical Health Questionnaire-9** (Kroenke et al., 2001)
  - **The Perceived Stress Scale** (Cohen et al., 1983)
  - **Friend Questions:** Participants were asked to indicate how long they had known their same-gender friend (who was enrolled to participate as an interaction partner at session 2), how long they had been friends with their same-gender friend, their relationship satisfaction with their same-gender friend, an inclusion of other in the self-scale (Aron et al., 1992) measuring perceived self-other overlap between them and their same-gender friend, and the extent to which they could rely on and count on their friend.
  - **Couples Satisfaction Index (CSI) scales** (Funk & Rogge, 2007)
  - **Revised Cheek and Buss Shyness Scale** (Hopko et al., 2005; Cheek, 1983)
  - **The Psychoticism Scale** (Eysenck et al., 1985)
  - **Revised UCLA Loneliness Scale** (Russell et al., 1980)
  - **Self-Construal Scale** (Park & Kitayama, 2014)
  - **The Experiences in Close Relationship Scale** (Wei et al., 2007)
  - **Positivity Resonance Scale (3-item version)** (Major et al., 2018)

## BODY AND SOCIAL BEHAVIOR (BSB)

- **Revised Self-Monitoring Scale** (Lennox & Wolfe, 1984)
- **Approach and Avoidance Motivation Scale** (Elliot et al., 2006)
- **Menstrual Status:** Participants indicated whether they menstruated, dates of their last and (anticipated) next period, cycle regularity, whether their cycle was predictable, and whether they took birth control. Menstrual day was calculated based on guidelines published in (Schmalenberger et al., 2021).
- **Traditional Masculinity and Femininity Scale** (Kachel et al., 2016)
- **Demographics:** Participants reported their age, sex, gender, race/ethnicity, sexual orientation, parental education, annual household income (for students, based on parents income), and subjective socioeconomic status and community status (Adler et al., 2000).
- **Heartbeat counting task** (Schandry, 1981): On each of 6 experimental trials, participants were asked to count their heartbeat for a variable period of time (25, 30, 35, 40, 45, and 50s in randomized order). After each trial, participants reported their subjective confidence in their count. Trials were interleaved with 30 second rest periods. This version of the Heartbeat counting task was implemented in Psychopy using scripts developed by (Legrand et al., 2022).

### Session 2

- **Self-report questionnaires:**
  - **Valence, Arousal, Dominance:** (same as above)
  - **Open ended feelings report:** (same as above)
  - **Sickness Symptoms:** (same as above)
  - **Daily Health Behaviors:** (same as above)
  - **Adapted Brief Pittsburgh Sleep Quality Index:** (same as above)
  - **Social Connection:** Participants responded to 10-items assessing feelings of social disconnection (adapted from Moieni et al., 2015).
  - **Modified Positive and Negative Affect Schedule (PANAS):** Participants rated the extent to which they were experiencing each of 30 emotion words ranging in both their valence and arousal. Words were taken primarily from the expanded version of the PANAS (David & Clark, 2011) and the State Trait Anxiety Inventory (Spielberger et al., 2017).
  - **Physical Symptoms Endorsements:** Participants rated the extent to which they were experiencing each of 12 physical symptoms (fidgety, muscle aches/pains, poor appetite, sluggish, drained, fatigued, energized, wide awake, restless, powerful, heavy, and weak).
  - **State Connectedness and Neediness** (Rude & Burnham, 1995)
  - **Friend Questions:** Participants were asked to indicate relationship satisfaction with their same-gender friend (same as above) as well as how much they had been co-present with their same-gender friend in the last 24 hours, and how connected to their friend they felt over the past 24 hours.
- **Sociogram task.** The sociogram task followed the standard protocol of the task (Kitayama et al., 2009). In the task, participants were told they would have five minutes to draw a picture of their social network using circles to symbolize each individual in the network and lines to symbolize a relationship between two members of the network, starting by placing themselves in the picture. Participants were instructed to only include the first and last initial and the gender identity (either Male, Non-binary, or Female). Participants were shown an example of a hypothetical network and then asked if they had any questions before starting on their own. On a standard sheet of printer paper, participants drew their sociogram for five minutes before they were asked to stop by the research assistant.

- **Social Interaction task.**
  - **Fast-Friends Procedure:** The fast friends procedure followed standard protocol of this task (Aron et al., 1997; Sprecher, 2020), in which two people engaged in a structured conversation for 12-15 minutes in-lab. The conversation was structured around one of two sets of 14 “get acquainted” questions (see Aron et al., 1997), in which participants alternated asking questions from a set of question cards. After reading a question, the other person first answered and then the question-asker answered the same question. We had two sets of question cards that were matched on intimacy and depth and were counterbalanced between the primary participant’s two interactions (with a close friend and stranger). The conversations were videorecorded, and physiology was assessed throughout.
  - **Pre-interaction survey:** Before the social interaction, participants independently and privately completed a set of items about anticipated feelings and expectations about the upcoming interaction. The set of items were drawn from existing work in relationship formation and relationship and affective science (e.g., IOS scale, see above; expected positivity resonance, adapted from Major et al., 2018). Social interaction partners were also asked about their prior night’s sleep (see above) and demographics (see above).
  - **Post-interaction Survey:** Immediately following the interaction, both participants in the social interaction completed a post-interaction survey, independently and privately (in their own room). The set of post-interaction items were drawn from existing work on impression formation, relationship initiation, and relationship and affective science (e.g., meta-perceptions of liking, Boothby et al., 2018; perceived similarity and self-disclosure, Sprecher, 2021; feelings of social connection, Inagaki et al., 2020; perceived partner responsiveness, Reis et al., 2017). Social interaction partners of the primary participant were also asked whether they thought the primary participant had received the influenza vaccine.
- **Bargaining game task.** Participants completed a two-part decision-making task adapted from standard protocols of behavioral economics games, including the Ultimatum Game and the Dictator Game (List, 2007; Nowak et al., 2000). In both parts of the task, participants played a bargaining game in which they were asked to make decisions about how to split different stakes of money between themselves and another person. On each of 90 experimental trials in the first part of the task, participants were asked to either “accept” or “reject” a money offer made by one of 90 different proposers on a stake of either \$9, \$10, or \$11. The proposed offers ranged from 10-50% of the stake. Participants were told that if they accepted an offer, then both them and the proposer would get the proposed split of money, and that if they rejected an offer, then neither them nor the proposer would get any money. In the second part of this task, participants took on the proposer role and were instructed to indicate how much of different money stakes they would like to offer to future responders in the study.
  - **Post-task survey:** Immediately following the task, participants reported their subjective ratings of five different offers they responded to during part one of the task. Specifically, for each of the five offers, participants were asked to write a couple of sentences answering what they thought about the offer and how the offer made them feel.
- **Debriefing.** Primary participants were debriefed at the end of the study, beginning with answering a few questions such as, 1) which vaccine condition do you think you were in?, 2) how confident are you that you were in that condition?, and 3) why do you think you

## BODY AND SOCIAL BEHAVIOR (BSB)

were in that condition? Then, participants were offered an opportunity to view and consent to additional uses of their video data. They were informed of their vaccine condition assignment at the end of the study and if they were in the placebo condition, given the opportunity to receive the influenza vaccine.

### 5. Analysis

**Transformations:** Cytokine measurements that were below the limit of detection for assay were replaced with the lower limit of detection value. Cytokine measurements that were detectable, but more than 3 standard deviations above the mean were winsorized and replaced with that value (i.e., *Mean + 3 SDs*). Then, values for IL-6, IL-10, IFN- $\gamma$ , and TNF- $\alpha$  were log-10 transformed. Inflammatory reactivity to the vaccine was computed as the change in log-transformed concentrations of circulating cytokines from pre- to post-vaccine.

**AMENDMENT 1: Testing for basic differences in physical symptoms, affectivity, and social connection.**

**1. Variables used**

- Demographic data
- S2 daily health behaviors
- Circulating concentrations of inflammation at session 1 and session 2
- Sickness Symptom Questionnaire (SicknessQ)
- Physical Symptom Endorsements for “Fatigue” and “Muscle aches/pains”
- Modified Positive and Negative Affect Schedule (PANAS)
- Adapted 5-item brief Pittsburgh Sleep Quality Index
- 10-items assessing social disconnection

**2. Analysis Plan**

**Statistical models:** Statistical models will assess 5 broad scientific aims.

**Scientific Aim 1: Inflammatory Cytokines.** To test whether treatment groups differed in circulating levels of pro-inflammatory cytokines following vaccine administration, we will run repeated-measures analyses of variance (RM-ANOVA; Winkens et al 2007). Inflammatory cytokines at both sessions will be treated as the criterion, session number (i.e., time) will be treated as a within-subjects predictor, and condition assignment (placebo vs. influenza vaccine) will be treated as a between-subjects predictor. RM-ANOVA models will be run separately for each of the four inflammatory cytokines assayed. Significance will be assessed at  $p<0.05$ . We hypothesize a significant interaction between condition and time on inflammation such that participants in the influenza condition will have higher levels of all four markers of inflammation than participants in the placebo condition at session 2 but not at session 1.

**Scientific Aim 2: Sickness Symptoms.** To test whether treatment groups differed in sickness symptoms following drug administration, we will complete a series of analytic steps:

1. Given that the Sickness Symptom Questionnaire (SicknessQ) has primarily been validated in samples treated with endotoxin (a potent inflammatory challenge), we will begin by conducting confirmatory factor analysis with 1 factor on scale items. Good model fit for CFA will be represented by  $RMSEA \leq .08$ ,  $CFI \geq .95$ , and  $TLI \geq .90$  (Hu & Bentler, 1999; Schreiber, Nora, Stage, Barlow, & King, 2006). We will then run t-tests to assess for group differences in overall sickness symptom scores. Significance for t-tests will be assessed at  $p<0.05$ .
2. We will also run separate two-tailed independent-samples t-tests to assess for group differences in individual sickness symptoms (i.e., each item of the SicknessQ). Significance will be assessed at  $p<0.05$ .
3. Finally, we will run two additional two-tailed independent-samples t-tests to assess for group differences in endorsements of two physical symptoms not included in the SicknessQ but commonly assessed when using this and similar methods (Eisenberger et al., 2009; Kuhlman et al., 2018): “*fatigue*” and “*muscle aches/pain*.” Significance will be assessed at  $p<0.05$ . Significance will be assessed at  $p<0.05$ .

**Scientific Aim 3. Affect.** To test whether treatment groups differed in felt affect following vaccine administration, we will run 4 two-tailed independent-samples t-tests to assess for group differences in positive high arousal (PH) affect, positive low arousal (PL) affect, negative high

## BODY AND SOCIAL BEHAVIOR (BSB)

(NH) arousal affect, and negative low (NL) arousal affect respectively. PH, PL, NH, and NL will be computed using the Positive and Negative Affect Schedule (PANAS) word endorsements. Specifically, PH will be operationalized as the mean endorsement across items: *amused, determined, enthusiastic, excited, happy, inspired, proud, strong, active, and alert*. PN will be operationalized as the mean endorsement across items: *Angry, Irritable, Nervous, Scared, Upset, Afraid, Ashamed, Distressed, Frustrated, Hostile, and Jittery*. NL will be operationalized as mean endorsement across items: *bored, guilty, sad, and worn out*. PL will be operationalized as mean endorsement across items: *attentive, calm, interested, grateful, and relieved*. Significance for t-tests will be assessed at  $p<0.05$ .

**Scientific aim 4. Sleep.** We will run three two-tailed independent-samples t-tests to assess for group differences in the subsequent night's sleep following vaccine-administration. First, we will assess for group differences in that night's sleep as operationalized using an index of items adapted from the Brief Pittsburgh Sleep Quality Index. These five items assess five facets of sleep—quality, quantity, daytime dysfunction, latency, and nighttime awakenings—and will be combined into a “Sleep Quality Index.” Next, we will run two additional models testing for group differences in two facets, subjective sleep quality (1-item) and subjective quantity (1-item), separately. Significance for all t-tests will be assessed at  $p<0.05$ .

**Scientific Aim 5. Social Connection.** We will run a two-tailed t-test to assess for group differences in felt social connection. Social connection will be operationalized as averaged scores on 10-items assessing feelings of social disconnection. Significance for t-tests will be assessed at  $p<0.05$ .

**Scientific Aim 6: Models using continuous measures of circulating cytokines.** To assess evidence for dose-dependency effects between circulating cytokines and outcomes-of-interest (same outcomes described in scientific aims 2-5), we will conduct a series of linear regression models using data from only the subset of participants assigned to the influenza vaccine condition ( $n=52$ ). Models will be run separately for each outcome-of-interest and for each cytokine and will take the general form:

1.  $outcome_i = \beta_0 + \beta_1(\Delta \text{inflammation}) + \beta_2(BL \text{inflammation})$
2.  $outcome_i = \beta_0 + \beta_1(\Delta \text{inflammation}) + \beta_2(BL \text{inflammation}) + \beta_3(ASAB) + \beta_4\left(\frac{\text{waist}}{\text{hip}}\right)$

\*Note that we will only control for baseline inflammation in models if baseline inflammation is significantly correlated with change in inflammation (Dalecki & Willits, 1991; Llabre et al., 1991; O'Connell et al., 2017).

Sensitivity analyses will also be run to assess whether results are robust when individuals are excluded who reported a diagnosis of depression ( $n=4$ ), took an SSRI the day of the session ( $n=4$ ), or who were non-compliant prior to study session 2 (3 participants drank alcohol and 5 participants took pain-killers). Sensitivity analyses will be run excluding groups one by one to maximize power.

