## **2. Design**

**Overview of Study design:** Participants completed two in-person study sessions ~24 hours apart. All study visits were scheduled in the morning (7:00 AM – 11:00 AM). During the first session (1-hour), participants completed informed consent, a self-report baseline questionnaire, and a heartbeat counting task. They also provided a baseline blood sample, collected via venipuncture, and were administered an injection of either the active influenza vaccine or a sham vaccine (saline solution). During the second session (2-hours), participants again completed self-report questionnaires and had their blood taken via venipuncture. They then completed three tasks: a sociogram task, two social interaction tasks, and a bargaining game task. Participants were then debriefed and compensated \$25/hour.

**Study type:** Experiment

**Randomization & Blinding:** Simple condition random assignment was implemented by UNC's Investigational Drug Services (IDS) pharmacy. Pre-filled (unlabeled) syringes were delivered by IDS to the University of North Carolina at Chapel Hill's Clinical and Translational research center (CTRC) in opaque stapled bags. These bags were opened by trained CTRC nursing staff—who dispensed the doses—immediately prior to drug injection. Primary research staff were not present for drug injection and participants were asked to look away during injection (and never saw the syringes) to maintain blinding.

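### Aim 6 applies a cytokine dose-dependency model to sleep on a night that ended before the only post-vaccine blood draw, so the sleep coefficients cannot carry a direction

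*Combined protocol and SAP*

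**What the plan says.** Amendment 1, Scientific Aim 6, states its purpose as "To assess evidence for dose-dependency effects between circulating cytokines and outcomes-of-interest". It uses the vaccine arm only (n=52) and runs a separate model for each outcome and each of the four cytokines. Form 1 has cytokine change and baseline cytokine as predictors. Form 2 adds assigned sex at birth and waist/hip ratio. A note keeps baseline cytokine only if it is significantly correlated with the change. Aim 6 covers the "same outcomes described in scientific aims 2-5), we will conduct a series of linear regression models".

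Aim 4 is therefore included. It sets out to "assess for group differences in the subsequent night's sleep following vaccine-administration", using a five-item index and "two facets, subjective sleep quality (1-item) and subjective quantity (1-item), separately".

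The main plan fixes the timing. Section 2 (Design) says "Participants completed two in-person study sessions ~24 hours apart", with all visits between 7:00 and 11:00 AM and the injection at session 1. On blood sampling it says "During the second session (2-hours), participants again completed self-report questionnaires and had their blood taken via venipuncture". Section 5 (Analysis, Transformations) defines reactivity as "the change in log-transformed concentrations of circulating cytokines from pre- to post-vaccine".

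**The concern.** One model form serves every outcome, with the cytokine change in the place of the dose. For sleep, the outcome is complete before the second half of that dose is sampled. A significant cytokine coefficient would naturally be read as larger inflammatory responses worsening sleep, yet the same coefficient would appear if a bad night altered the next morning's cytokines. At stake is a directional statement about sleep that the sampling times do not support. It would come from a registered analysis and so carry more weight than an exploratory correlation.

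**Working it through.** **The plan's own figure.** The Power section of Amendment 1 gives a detectable f² of 0.16 for this regression (n=52, 4 predictors, two-tailed alpha 0.05, 80% power). Using a noncentral t with noncentrality √(f²·n) and 52 − 4 − 1 = 47 degrees of freedom, 80% power is reached at f² = 0.157, which rounds to 0.16. The figure is reproduced and has no bearing on direction.

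**Time order.**

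| Event | When | Source |
|---|---|---|
| Baseline blood, injection | Session 1, morning | Section 2 |
| Night rated in Aim 4 | Between the sessions | Amendment 1, Aim 4 |
| Post-vaccine blood | Session 2, next morning | Section 2 |
| Cytokine change | Available only after the session 2 draw | Section 5 |
| Symptom, affect and connection ratings | Session 2, close to the draw | Sections 2 and 4 |

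There are only two draws. The interval over which change is measured starts before the night and contains it. Cytokines may have risen first and disturbed sleep, or sleep may have been poor first and moved the cytokines. One post-injection sample cannot tell these apart.

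**Fits affected.** 3 sleep outcomes (index, quality, quantity) x 4 cytokines = 12 pairs; 12 x 2 model forms = 24 fits. The index also holds a daytime dysfunction item, which may not be confined to the night. The quality and quantity items are about the night.

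**What in Aim 6 could settle direction.**
- Randomisation does not help, because only the vaccine arm is used.
- The covariates are baseline cytokine (conditionally), assigned sex and waist/hip ratio. Session 1 sleep was collected (section 4, Session 1) but is not in the models. Adding it could account for habitual differences in sleep, but it would not order the events of that night.
- The sensitivity exclusions (depression diagnosis, SSRI use, alcohol, pain-killers) do not concern direction.

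**Does turning the model round help?** Write B for baseline and P for session 2 log cytokine. Form 1 is

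sleep = β0 + β1(P − B) + β2·B = β0 + β1·P + (β2 − β1)·B.

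So β1 is the coefficient of P given B. Its test statistic is t = r·√(df/(1 − r²)), where r is the partial correlation of sleep and P given B, and df = 52 − 3 = 49. The model P = γ0 + γ1·sleep + γ2·B tests the same r with the same df, so t and p are identical. With the two extra covariates in both directions the identity still holds, with df = 52 − 5 = 47. Numerical checks at n=52 agreed: p-values from the two directions differed by about 1e-14 in form 1, and one dataset with two extra covariates gave p = 0.0127 both ways.

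The two directions differ only where the baseline rule drops B. The planned model then tests the correlation of sleep with P − B, which is a different quantity from r.

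**The case against.** **The wording is loose.** Aim 6 speaks of effects between cytokines and outcomes and, unlike Aim 1, states no directional hypothesis. That is so. But dose-dependency, with cytokine change as the predictor, treats the cytokine as the dose, and nothing in the plan limits the reading to an undirected association.

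**The causal question on sleep is answered elsewhere.** The Aim 4 t-tests compare randomised arms. This stands for the effect of vaccination on sleep, and a reader should not infer that those tests are weakened. They do not support a statement that the size of the cytokine response drives sleep.

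**The other outcomes share the weakness.** Symptoms, affect and connection are rated at session 2, next to a single post-injection draw, so they are only concurrent with it. This also stands: keeping the claim for Aims 2, 3 and 5 does not certify its direction. Sleep differs in that the period rated is already over at the draw.

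**Stronger readings.** A reader might infer that the time order is reversed and that the model must be turned round. The documents do not support this: the change interval contains the night, so the order is undetermined, and turning the model round alters no p-value while baseline is included. A reader might also infer an inflated false-positive rate. Simulating an effect of sleep on cytokines does make the cytokine term significant more than 5% of the time, but that is power to detect an association built into the data, so 5% is the wrong comparator. Nor do the documents say that poor sleep moves these cytokines.

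**Conclusion.** The concern holds as a limit on interpretation. For the 24 sleep fits, the design supports an association between that night's sleep and session 2 cytokines, and no direction. This rests only on the documented visit times, the definition of change and the scope of Aim 6; it needs no assumed size for an effect of sleep on cytokines. It is not an error in the test or in the power calculation. The weight is moderate: the analysis is secondary, but an unsupported directional reading would be registered in advance and is easily removed.

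**What to change.** In Scientific Aim 6, limit the dose-dependency claim to the outcomes of Aims 2, 3 and 5, and say that those ratings are concurrent with the session 2 draw. Add that the sleep models are reported as undirected associations between the night after injection and session 2 cytokines, and note that the daytime dysfunction item in the index may extend beyond the night.

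For the sleep models, always keep baseline log cytokine, so that all four cytokines address the same quantity whatever the baseline correlation test shows. Writing session 2 cytokine as the response is optional; with baseline included it changes the estimand and the label, not the t-statistic or p-value.

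The cost is a few sentences in Amendment 1 and, where the rule would have dropped baseline, a refit on data already held. The sponsor gives up a directional claim on sleep in a secondary analysis.

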## BODY AND SOCIAL BEHAVIOR (BSB)

$n_{participants}=102$ ,  $r=0.5$ , suggested that we would be adequately powered to observe a medium effect size  $f^2=0.14$ .

Sensitivity Analysis for t-tests: Sensitivity analysis conducted in g\*power for a two-tailed t-test (independent means) with  $\alpha=0.05$ ,  $(1-\beta)=0.80$ ,  $n_1=50$ ,  $n_2=52$  suggested that we would be adequately powered to observe a medium effect size  $d=0.56$ .

Sensitivity Analysis for linear regression: Sensitivity analysis for simple regression (fixed model, single regression coefficient) for a two-tailed t-test with  $\alpha=0.05$ ,  $(1-\beta)=0.80$ ,  $n_{participants}=52$ , and  $n_{predictors}=4$  suggested that we would be adequately powered to observe a medium effect size  $f^2=0.16$ .

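### Aim 6 looks for cytokine dose-dependency in the vaccine arm only, so its slopes cannot show whether an association goes beyond one also present under placebo

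*Combined protocol and SAP*

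**What the plan says.** Aim 6 (Amendment 1, section 2, Analysis Plan) gives its purpose as "To assess evidence for dose-dependency effects between circulating cytokines and outcomes-of-interest", where the outcomes are those of Aims 2 to 5. The regressions are fitted "using data from only the subset of participants assigned to the influenza vaccine condition", which is 52 people. "Models will be run separately for each outcome-of-interest and for each cytokine and will take the general form" of two equations. The first has cytokine change and baseline cytokine. The second adds assigned sex at birth and waist/hip ratio. Baseline is kept only if it correlates significantly with change. Neither equation has a condition term or a change-by-condition term. The sensitivity analyses that follow are exclusions only (depression diagnosis, SSRI use, alcohol, painkillers).

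The main document, section 5 (Analysis), names the predictor: "Inflammatory reactivity to the vaccine was computed as the change in log-transformed concentrations of circulating cytokines from pre- to post-vaccine". Section 4 (Manipulated variables) describes blood sampling for all participants: "At both sessions 1 and 2, approximately 6 mL of blood were collected via venipuncture". The Session 2 questionnaires are likewise not restricted by arm, and Aims 2 to 5 compare the arms on these same outcomes. The placebo data needed for a comparison therefore exist.

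**The concern.** Change in a cytokine over about 24 hours mixes any response to the injection with ordinary fluctuation and assay noise. Either of the first two could go along with poor sleep, low mood or malaise. The plan allows for other influences through its covariates and exclusions, but it leaves out the most direct evidence on background association: the same slope in people who received saline.

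Aims 1 to 5 do not fill this gap. They compare arms on cytokines and on outcomes, and never ask whether the cytokine-outcome slope differs by arm.

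At stake is what Aim 6 can conclude. It covers 11 outcomes (SicknessQ total, fatigue, muscle aches, four affect scores, three sleep scores, social connection: 1+2+4+3+1) and four cytokines. That is at least 11 × 4 = 44 slopes per model form, before the individual SicknessQ items. With the predictor named as reactivity to the vaccine, a significant slope invites a vaccine-specific reading that the model has not tested.

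**Working it through.** **Inputs from the documents.** Vaccine arm 52, hence placebo 50 (the t-test sensitivity analysis uses 50 and 52). The Aim 6 sensitivity figure is described as "Sensitivity analysis for simple regression (fixed model, single regression coefficient) for a two-tailed t-test", with alpha 0.05, power 0.80, 52 participants, 4 predictors and a detectable f² of 0.16.

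**Inputs assumed.** Correlations, slopes and SDs of change. The documents give none, so ranges are shown.

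**1. The plan's own figure.** For one coefficient, ncp = √(f²·N) and df = N − p − 1. With f² = 0.16, ncp = √(0.16 × 52) = 2.88 and df = 52 − 4 − 1 = 47, which gives power 0.807. The smallest f² with 80% power is 0.157. The stated 0.16 is reproduced.

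**2. What the planned test responds to.** It uses no placebo data, so its rejection rate depends only on the vaccine-arm association. Simulation of 50 placebo and 52 vaccine participants, standardised change and outcome, equal SD of change, two-sided 0.05 (repeated runs agree within about two percentage points):

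| Assumed truth | Vaccine-only slope significant | Change-by-condition significant |
|---|---|---|
| Same r in both arms: 0.2 / 0.3 / 0.4 | 29% / 58% / 86% | about 5% at each |
| Vaccine arm only: r = 0.3 / 0.4 / 0.5 | 60% / 86% / 97% | 32% / 52% / 75% |

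At r = 0.3 the planned test gives nearly the same rate (58% and 60%) under both truths. A second simulation used the second equation's covariates, with a slope of 0.4 and residual SD 1 (f² = 0.4² = 0.16). It agrees: about 76% with an equal placebo slope and 77% with a zero placebo slope, while the interaction was significant in about 5% and 49%.

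**3. Type I error.** With a true slope of zero in the vaccine arm, the planned test rejected in 4.6% of runs. Its level is intact.

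**4. How precise the slope comparison would be.** With standardised change and residual SD 1, SE of the slope difference = √(1/52 + 1/50) = 0.198, with df = 102 − 7 = 95. For a difference of 0.4, ncp = 0.4/0.198 = 2.02 and power is 52%. Power of 80% needs a difference of about 0.56. If the placebo SD of change is half the vaccine-arm SD, SE = √(1/52 + 1/(50 × 0.25)) = 0.315, and 80% power needs about 0.89.

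**5. Dependence on equal SDs.** With the placebo SD halved, interaction power at r = 0.3 / 0.4 / 0.5 (vaccine arm only) falls to about 16% / 26% / 40%. Equal correlations then no longer mean equal slopes: the placebo slope is twice as steep, and the interaction rejects in about 10% / 16% / 27% at r = 0.2 / 0.3 / 0.4. When it is the slopes that are equal, the rate stays near 5%.

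**6. A true cytokine effect common to both arms.** Let the vaccine raise change by 1 SD and let cytokines cause the outcome with the same slope in both arms. The vaccine-only slope is significant in about 29% / 60% / 84% at r = 0.2 / 0.3 / 0.4. The interaction is significant in about 5%, and in the direction of a steeper vaccine slope in only 2% to 3%.

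**The case against.** The dose in Aim 6 is the circulating cytokine, not the injection, so it does not matter that everyone in the arm received the same volume. The plan nowhere states that a slope would show a vaccine effect, and the phrase about reactivity names a change score. The randomised evidence is in Aims 1 to 5, and Aim 6 comes last, with some covariates and exclusions against confounding. Restricting to the challenged arm is a defensible way to study reactivity. All of this is fair, and it keeps the point to one of interpretation.

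Two stronger readings are tempting, and neither is supported.

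- A reader might take the 58% as a false-positive rate. It is not. Step 6 gives much the same rate where cytokines really do cause the outcome, and step 3 shows that the level of the test holds.
- A reader might infer that dose-dependency should be claimed only where the vaccine slope exceeds the placebo slope. If cytokines cause symptoms and the vaccine acts by raising cytokines, equal slopes per unit of cytokine are what one expects. Such a rule would withhold the term about 97% of the time in step 6. Nor does an interaction remove confounding of a non-randomised predictor.

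What remains is that the plan has the placebo slope available, does not report it, and so leaves the reader unable to judge whether the vaccine-arm association is anything more than background.

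**Conclusion.** The point holds as a limit on what Aim 6 can conclude. A vaccine-arm slope alone is a within-arm association. It does not show whether the association reflects vaccine-evoked change or one that is also present under placebo, because the planned test rejects about equally often in both situations (about 58% at r = 0.3). The planned test is valid for the question of whether the vaccine-arm slope is zero, and the randomised comparisons in Aims 1 to 5 are unaffected.

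The percentages rest on assumed correlations. The figures for the interaction also rest on assumed SDs of change, and they worsen if change varies less under placebo. An equal placebo slope would not refute a general cytokine-outcome relation; it would show only that the relation is not specific to the vaccine arm.

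**What to change.** Keep the planned models and add the following to Aim 6:

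- Fit the identical models, with the same covariate set, in the 50 placebo participants as a comparator.
- Fit a pooled model in all 102: outcome on change, baseline, condition and change × condition, with sex and waist/hip ratio added in the second form.
- For each outcome and cytokine, report both slopes and the slope difference with its 95% confidence interval.
- Describe a vaccine-arm slope as a within-arm association and state whether a similar slope is seen under placebo. Where the interval for the difference is wide, say that specificity to the vaccine is undetermined.
- Leave causal statements about the vaccine to Aims 1 to 5.
- Mark these analyses as added after data access, since section 3 (Existing data) states that the data exist and have been accessed.

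The cost is a few sentences in the plan and more model runs on data already collected. The drawback is low power for the slope difference: about 32%, 52% and 75% at r = 0.3, 0.4 and 0.5 with equal SDs, and about 16%, 26% and 40% if the placebo SD of change is half as large. For that reason the report should rest on the estimates and intervals and not on whether the interaction is significant.
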